6.2 Guidelines for Dose Modifications

Toxicities and dose modifications (refer to section 6.3) will be monitored in all cycles. Adjustments to the doses of study drug will be based upon toxicity, graded according to the NCI Common Toxicity Criteria (CTC), Version 4.0, if these were normal at baseline. Events that are not described in the NCI criteria will be assigned grades according to the criteria provided in Section 8.0. Criteria for determining the relatedness of clinical adverse events to treatment (Section 8.0) should be utilized to determine the relationship of adverse events to the treatment.

6.3 Dose Modification

Patients experiencing any toxicity specified below attributable to DFMO or any intolerable toxicity will have their dose of DFMO held until toxicities have reverted to \leq Grade 2 toxicity (with the exceptions below for neutropenia, thrombocytopenia and transaminases). Upon resolution of the toxicity, subjects will receive a dose reduction of DFMO to one step down on the dosing table in section 6.1.2 (one less tablet per dose than their current dose). Subjects that are currently only taking one tablet per dose BID will be dose reduced to one tablet per day (QD). Subjects will be allowed to dose reduce for subsequent toxicities defined here as many times as they can until they reach the one tablet per day (QD) dosing. At that point if they experience another dose reducing toxicity (as defined here) they will be required to go off protocol therapy.

- Grade 4 neutropenia or thrombocytopenia that persists for 7 days or longer after holding study drug. (DFMO should be held as soon as a Grade 4 related neutropenia is discovered. Subject will only dose reduced if toxicity persists at a Grade 4 for longer than 7 days after the hold starts. If subject resolves before 7 days of hold they will resume at previous dose. If subject does not resolve after 14 days of a hold they will be discontinued from study).
- >10 X elevation of transaminases that persists for 7 days or longer after holding study drug. (DFMO should be held as soon as a 10X related elevation is discovered. Subject will only dose reduced if toxicity persists at >10 X ULN or higher for longer than 7 days after the hold starts. If subject resolves before 7 days of hold they will resume at previous dose. If subject does not resolve to <10 x ULN after 14 days of a hold they will be discontinued from study).
- Any other Grade 3 non-hematologic toxicity, excluding alopecia, nausea, vomiting, and diarrhea that does not adequately respond to treatment.

If there is no resolution of above toxicity by 14 days, DFMO should be discontinued, and subjects should be discontinued from the study.

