Pregnancy and Lactation: Pregnancy category C. It is unknown if eflornithine crosses the placenta. Case reports in humans along with animal studies (mice, rats) indicate potential for fetotoxicity. Experiments in rodents indicate that eflornithine blocks yolk sac formation and trophoblast differentiation, affecting processes such as vasculogenesis and steroidogenesis (Lopez-

Garcia, *et al.*, 2008). The World Health Organization has not determined a breast feeding rating for eflornithine due to insufficient data. The Thompson lactation rating is that infant risk cannot be ruled out. No studies investigating the safety of lactation after eflornithine administration have been conducted, nor are there data to determine drug levels in breast milk after drug administration.

Toxicity for DFMO Potential Risk:

Likely Happens to 10-30 patients out of every 100
	
Less Likely Happens to 3-10 patients out of every 100
	
Rare Happens to fewer than 3 patients out of every 100

 • Fewer red and white blood cells 
 ○ a low number of red blood cells can make you feel tired and weak and may require transfusion. ○ a low number of white blood cells can make it easier to get infections • Decrease in the number of platelets made in the bone marrow 	
 • Nausea • Hearing Loss • Ringing in ears • Diarrhea • Headache • Weakness 	
 • Loss of appetite • Abdominal Pain • Flatulence (gas) • Dizziness • • Skin Rash • Seizures • Sores in the mouth • Runny nose • Difficulty sleeping • Infections • Dry mouth • Constipation • Dry skin • Menstrual disorders • Sore throat • Vomiting • Vasodilation (the relaxation of blood vessels possibly causing low blood pressure) • Emotional ups and downs • Itchiness • Body aches • Pain

Four particular areas of concern have been identified with regard to the safety of subjects participating in this study and an attempt to address each of them is outlined below: The main considerations are: thrombocytopenia, hearing loss, gastrointestinal and non-G.I. side effects.

a) DFMO Specific Adverse Events

(1) Hearing loss.

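### Section 6.3 gives incomplete or conflicting instructions on holding and reducing DFMO: for Grade 4 thrombocytopenia, Grade 4 non-hematologic toxicity, recovery on day 7 of a hold, and refractory gastrointestinal events

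*Combined protocol and SAP*

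**What the plan says.** Section 6.3 opens with a general rule: "Patients experiencing any toxicity specified below attributable to DFMO or any intolerable toxicity will have their dose of DFMO held". Drug stays on hold until the toxicity has fallen to Grade 2 or lower, "with the exceptions below for neutropenia, thrombocytopenia and transaminases". On resolution the subject restarts one tablet per dose lower, or goes from one tablet twice daily to one tablet once daily. A subject already on one tablet daily who has a further dose-reducing toxicity, as 6.3 defines it, leaves protocol therapy. Three bullets then list the toxicities.

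- **Hematologic.** The heading is "Grade 4 neutropenia or thrombocytopenia that persists for 7 days or longer after holding study drug". The parenthesis that follows says "DFMO should be held as soon as a Grade 4 related neutropenia is discovered", then "Subject will only dose reduced if toxicity persists at a Grade 4 for longer than 7 days after the hold starts", then "If subject resolves before 7 days of hold they will resume at previous dose". A subject not resolved after 14 days of hold is discontinued.
- **Transaminases above 10 times the upper limit.** The structure and the 7-day and 14-day wording are the same, but the hold-on-discovery sentence names the toxicity in its own heading.
- **Other non-hematologic.** "Any other Grade 3 non-hematologic toxicity, excluding alopecia, nausea, vomiting, and diarrhea that does not adequately respond to treatment".

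A closing sentence discontinues any subject whose listed toxicity has not resolved by 14 days.

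Section 6.1.6 names the safety concerns: "The main considerations are: thrombocytopenia, hearing loss, gastrointestinal and non-G.I. side effects". The synopsis (Criteria for Evaluation) makes the frequency of dose interruptions, reductions and treatment discontinuation part of the safety analysis.

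**The concern.** These are operative safety rules, to be applied over 27 cycles at up to 25 sites. A site applying them literally meets four places where the text is silent, circular or contradictory. One concerns thrombocytopenia and another gastrointestinal events, both of which section 6.1.6 lists as main considerations. Two sites could treat the same event differently, and both could claim to have followed the protocol.

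The reported safety results are affected too. Interruptions, reductions and discontinuations are counted and summarized, so differences in how sites read 6.3 become part of the apparent tolerability of the drug.

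**Working it through.** No sample size, power or error rate is involved. The check sets the clauses of 6.3 side by side and looks elsewhere in the protocol for text that settles them.

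**1. Hold on discovery**

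| Toxicity | In a bullet heading? | Heading presupposes a hold? | Named in a hold-on-discovery sentence? |
|---|---|---|---|
| Grade 4 neutropenia | yes | yes | yes |
| Grade 4 thrombocytopenia | yes | yes | **no** |
| Transaminases above 10 times the limit | yes | yes | yes |

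The general rule holds drug for a listed toxicity, and the listed toxicity is one that persists after drug has been held. The discovery sentence breaks this circle for two of the three laboratory toxicities. For thrombocytopenia the hold must be inferred from the heading or from the intolerable-toxicity wording.

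**2. Non-hematologic Grade 4**

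The bullet names Grade 3 and does not add higher grades. Tracing a Grade 4 event through the section:

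- Hold and reduction: reached only if the event is judged intolerable, a term that 6.3 does not define.
- Leaving therapy at the one-tablet-daily level: requires a dose-reducing toxicity as defined in 6.3. Whether Grade 4 qualifies is unclear.
- The closing 14-day rule: refers to the toxicities listed above it. Whether Grade 4 is among them is unclear.

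**3. The 7-day limit**

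Let T be the number of days from the start of the hold to resolution. The same table applies to the hematologic and transaminase bullets.

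| T | Heading (T at least 7) | Reduction clause (only if T above 7) | Resume clause (T below 7) | Result |
|---|---|---|---|---|
| below 7 | not met | not met | met | previous dose; clauses agree |
| exactly 7 | **met** | **not met** | **not met** | heading says reduce, parenthesis forbids it, resume clause does not apply |
| above 7, up to 14 | met | met | not met | reduce; clauses agree |

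Since the reduction is made on resolution, a patient still at Grade 4 on day 7 remains on hold under every clause. The conflict is confined to T = 7.

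The size of the step at stake follows from the tablet counts in section 6.1.2:

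- 4 to 3 tablets per dose: 1/4 = 25%
- 3 to 2: 1/3 = 33%
- 2 to 1: 1/2 = 50%
- 1 twice daily to 1 once daily: 1/2 = 50%

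**4. The gastrointestinal exclusion**

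The final clause of the last bullet, about inadequate response to treatment, can attach in more than one way:

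- If it qualifies the excluded events, those that fail to respond are the ones exempted.
- If it limits the exclusion, events that fail to respond are brought back in.
- If it qualifies the toxicity at the start of the sentence, the named events are excluded whether or not they respond.

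The grammar does not settle which is meant.

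**Other sections**

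Section 6.2 refers back to 6.3. Section 9.1 permits the investigator to take a subject off therapy for an adverse event, but it contains no hold or reduction rule. Neither resolves any of the four points.

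**The case against.** The best defense is that a sensible investigator would not go wrong.

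**Thrombocytopenia.** A reader might infer that 6.3 never starts a hold for Grade 4 thrombocytopenia. The text does not support that. The general rule covers intolerable toxicity and names thrombocytopenia among the toxicities with their own provisions, and the bullet heading takes it for granted that drug is held. What stands is narrower: there is no explicit hold-on-discovery instruction for it, although there is one for each of the other two laboratory toxicities.

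**Frequency.** The risk table in section 6.1.6 puts platelet decrease at 10 to 30 per 100, but without a grade, so it cannot size a Grade 4 problem. The same section says myelosuppression is not usual at the low dose used here and links thrombocytopenia mainly to doses above 3 g/m²/day. The top of the stated range is 2 × 1000 = 2000 mg/m²/day. Against that, the section also links it to cancer patients with previous chemotherapy, which describes this population. The frequency remains unknown.

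**Grade 4 non-hematologic events.** Holding at Grade 3 and continuing at Grade 4 would be a strained reading, and the intolerable-toxicity wording makes it avoidable. That answers the hold. It does not answer whether the off-therapy and 14-day rules apply.

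**Day 7.** A reader might infer that every patient assessed on day 7 receives contradictory orders. Only one who resolves exactly then does. Day 7 would be a natural recheck day if counts were repeated weekly, but 6.3 sets no recheck interval and the scheduled counts are not weekly.

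**Gastrointestinal events.** It is tempting to say that refractory events are plainly exempted. The sentence is ambiguous and allows the opposite reading as well.

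**Consequences.** The trial has a single arm, so uneven handling cannot bias a comparison between arms. Dose-modification counts are descriptive and already depend on investigator judgment. This limits the severity but leaves the text unreconciled.

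**Conclusion.** Section 6.3 is internally inconsistent on four points: the missing hold-on-discovery instruction for Grade 4 thrombocytopenia, the unclear status of Grade 4 non-hematologic toxicity, the mismatched 7-day limits in two bullets, and the ambiguous gastrointestinal exclusion. All four follow from the wording alone. The day-7 point further assumes that a toxicity clearing on day 7 of a hold counts as having lasted 7 days.

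Severity is moderate. For a patient who resolves on day 7 the difference is the previous dose or a reduction of 25% to 50%. How many patients would be affected by any of the four cannot be derived, because the protocol gives no Grade 4 rates and no recheck schedule during a hold. The effects are on patient handling and on the counts of interruptions, reductions and discontinuations. The EFS test, sample size and power are unaffected.

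**What to change.** The sponsor should reconcile the sentences of section 6.3 so that:

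- the hold-on-discovery sentence in the hematologic bullet matches the toxicities in its heading;
- the last bullet states which grades it covers, and the off-therapy and 14-day rules make clear whether they apply to the same set;
- the heading, reduction clause and resume clause use one consistent 7-day boundary in both the hematologic and transaminase bullets, so that resolution on day 7 has exactly one outcome;
- the last bullet states unambiguously how the gastrointestinal exclusion applies to events that do not respond to treatment.

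The clinical content of each rule is for the sponsor to decide; what is asked is that the sentences agree. The cost is a wording amendment to one section and a memo to sites, with no added visits or tests.

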7.10 Survival Follow-up

Subjects will be followed for long term survival by contact with parent or treating institution to confirm survival at the following time points (time from last dose of study drug):

- | | |
|-------------|-------------------------------------|
| - 6 months | -2 years |
| - 1 year | -Yearly after (up to 5 years total) |
| - 18 months | |

Follow up will continue for five (5) years off-therapy or until subject death or subject is lost to follow up (per definition in section 9.0). The follow-up results including follow-up status, remission status, and date of death will be recorded on the appropriate page of the CRF, as well as in the subject's source documentation.

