9.0 Patient Withdrawal and Trial Discontinuation

9.1 Criteria for Subject Off-Therapy

Subjects may be withdrawn from the study treatment for the following reasons:

- Subject completes all protocol defined therapy- 27 cycles
- Relapsed neoplastic disease
- Subject or guardian withdraws consent to continue study drug
- Subject develops an intercurrent illness that precludes further participation, or requires a prohibited concomitant treatment
- The Investigator withdraws the subject in the subject's best interests
- Subject is lost to follow-up (defined as the inability to contact the subject on 3 separate occasions over a period of 2 weeks)
- Administrative reasons (e.g., the subject is transferred to hospice care)
- An adverse event, which in the opinion of the Investigator, precludes further trial participation or fulfills the protocol requirements for withdrawal (e.g., the development of dose limiting toxicity despite a reduction in protocol therapy for a previous episode of dose limiting toxicity)
- Death

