9.2 Criteria for Subject Off-Study

Subjects may be withdrawn from the study completely which includes survival follow-up for the following reasons:

- Subject or guardian withdraws consent to continue in the trial
- Subject is lost to follow-up (defined as the inability to contact the subject on 3 separate occasions over a period of 2 weeks)
- Subject completes all protocol defined therapy including all follow-up time points.
- Death

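### Section 6.3 takes subjects with unresolved toxicity off the study, while sections 7.10, 9.1 and 9.2 point to off therapy with follow-up continuing; read literally, 6.3 could censor EFS and OS at toxicity

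*Combined protocol and SAP*

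**What the plan says.** Section 6.3 (Dose Modification) deals with unresolved toxicity in three places. The neutropenia and thrombocytopenia bullet says "If subject does not resolve after 14 days of a hold they will be discontinued from study". The transaminase bullet is nearly identical. The closing sentence covers all the listed toxicities: "DFMO should be discontinued, and subjects should be discontinued from the study".

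The same section uses a different term for another toxicity exit. A subject already at the lowest dose level who has a further qualifying toxicity is handled thus: "they will be required to go off protocol therapy".

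Three other sections bear on what happens next:

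- **9.1 (off-therapy).** The reasons for stopping study treatment include "An adverse event, which in the opinion of the Investigator, precludes further trial participation or fulfills the protocol requirements for withdrawal".
- **9.2 (off-study).** The list opens "Subjects may be withdrawn from the study completely which includes survival follow-up for the following reasons". It has four entries: withdrawal of consent, loss to follow-up, completion of therapy and all follow-up, and death. Toxicity is not one of them.
- **7.10 (survival follow-up).** "Follow up will continue for five (5) years off-therapy", ending earlier only at death or loss to follow-up. Remission status and date of death are recorded.

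Sections 10.4 and 10.5 censor EFS and OS at last contact when no event has been seen.

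**The concern.** The closing sentence of 6.3 names stopping the drug and leaving the study as two separate acts, and the section elsewhere has its own term for stopping therapy alone. So the word study in 6.3 is hard to read as shorthand for drug. Under the definition in 9.2, leaving the study ends survival follow-up.

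A site applying 6.3 in that sense would stop observing a subject at the point where DFMO is stopped for toxicity. Any later relapse or death would go unrecorded, and EFS (primary) and OS (secondary) would be censored there. These subjects are selected by toxicity and by having stopped treatment, so the censoring may be informative. It is informative only if their relapse or death risk differs from that of the others. The trial has a single arm tested against a fixed 70%, so no control group would share the distortion.

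The Stratum 1 test is a binomial test of two-year status, and the plan has no rule for a subject whose two-year status is unknown. A subject lost this way has to be dropped, counted as a failure or counted as event-free, and the choice changes the operating characteristics.

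**Working it through.** **The texts side by side**

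| Section | Status of a subject with toxicity unresolved at 14 days | Follow-up implied |
|---|---|---|
| 6.3, two bullets and closing sentence | Off study | Ends, under the 9.2 definition |
| 9.1 | Adverse event is an off-therapy reason | Continues under 7.10 |
| 9.2 | Toxicity not among the off-study reasons | No basis for ending it |
| 7.10 | Off therapy | Five years, until death or loss to follow-up |

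Sections 8.2 and 8.3 pull the same way as 7.10: adverse events are followed to baseline or grade 2 or below, and serious events to resolution or stabilization. That is hard to do for a subject who has left the study with the toxicity unresolved.

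**Reproducing the plan's figure**

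Inputs, from the synopsis and section 10 (Sample Size and Analysis, Stratum 1): n = 127 evaluable, one-sided 5% one-sample binomial test, 70% against 80%, 80% power. With X the number event-free at two years, the smallest cutoff r with P(X ≥ r | 127, 0.70) ≤ 0.05 is r = 98:

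- alpha = P(X ≥ 98 | 127, 0.70) = 0.045
- power = P(X ≥ 98 | 127, 0.80) = 0.820

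The planned sample size reproduces and is not in dispute.

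**How much lost status could matter**

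The documents give no rate for this exit, so a fraction c of 3% or 5% is assumed. 127 × 0.03 = 3.8 subjects, about 4; 127 × 0.05 = 6.4, about 6.

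1. *Dropped from the denominator, cutoff recomputed.* This takes the lost subjects to be no different from the rest.
   - 123 left: r = 95, alpha 0.047, power 0.812.
   - 121 left: r = 94, alpha 0.038, power 0.776.
   - Part of the difference comes from the discreteness of the exact test: at 124 left, power is 0.799.
2. *All counted as failures, cutoff kept at 98.* Success probability under the alternative becomes 0.80 × (1 − c).
   - c = 3%: 0.80 × 0.97 = 0.776, power 0.596.
   - c = 5%: 0.80 × 0.95 = 0.760, power 0.426.
   - At c = 1%: 0.80 × 0.99 = 0.792, power 0.754.
3. *All counted as event-free, cutoff kept at 98.* Success probability under the null becomes 0.70 + 0.30 × c.
   - c = 3%: 0.709, true alpha 0.070.
   - c = 5%: 0.715, true alpha 0.092.

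Cases 2 and 3 are bounds. No section says that unknown status counts as failure or as success.

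**Bias if the lost subjects differ**

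Suppose the true two-year EFS is 60% in those lost and 80% in the rest (assumption). An estimate from the rest alone is 80%. The truth is 0.95 × 80% + 0.05 × 60% = 79% at c = 5%, and 0.97 × 80% + 0.03 × 60% = 79.4% at c = 3%. The estimate is too high by 1.0 or 0.6 percentage points.

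**The case against.** A reader might infer that 6.3 is certain to end follow-up for these subjects. The documents do not support that. Section 9.1 places an adverse event that meets the protocol's withdrawal requirements under off-therapy, which naturally covers the 6.3 exit and suggests that the protocol uses such words loosely for stopping the drug. Section 7.10 stops follow-up only at death or loss to follow-up, and 9.2 is permissive in wording. A site following 7.10 and 9.1 would lose nothing. This objection stands: the fault is conflicting instructions, and loss of data is a possible consequence.

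A reader might also take 0.60 and 0.43 as the expected power. They require every lost subject to be scored as a failure, which the plan does not specify; section 10.4 censors at last contact. Dropping the subjects costs far less.

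The 3% and 5% rates are assumptions. The exit requires toxicity that outlasts a 14-day hold, which is narrower than toxicity in general. Section 6.1.6 says myelosuppression is not usual at the low dose, while its risk table puts low blood counts among the likely effects. Neither gives a rate of non-resolution at 14 days.

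None of this removes the contradiction. Section 6.3 is where a site looks when toxicity occurs, and up to 25 sites may resolve the conflict differently.

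**Conclusion.** Section 6.3 contradicts 7.10, 9.1 and 9.2 on whether a subject with toxicity unresolved at 14 days remains under follow-up, and the text is wrong as written. Taken literally, 6.3 could lead a site to censor EFS and OS at toxicity, with bias only if these subjects' risk differs.

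The likely effect is small to moderate: for an assumed loss of 3% or 5%, power of about 0.81 or 0.78 against 0.82 if the subjects are dropped, and a shift in estimated EFS of about one percentage point or less under the assumed 20-point difference. The bounds are wider: power of 0.60 or 0.43 if all are failures, alpha of about 0.07 or 0.09 if all are event-free. The true rate of exit by this route is unknown.

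It would be too strong to conclude that correcting 6.3 secures complete EFS data. Follow-up under 7.10 is by contact with the parent or treating institution, with no scheduled scans after the off-therapy visit. In addition, a subject who leaves before the first evaluation (generally 3 cycles) without progression falls outside the efficacy population in section 10.2, whatever 6.3 says.

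**What to change.** Reconcile section 6.3, in all three places, with 7.10, 9.1 and 9.2, so that the follow-up status of this exit is off protocol therapy, with remission status and survival still collected as 7.10 already provides. The toxicity thresholds, hold periods and dose rules are not at issue, and no change to them is suggested.

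The cost is a wording amendment. It needs no new visits and leaves n = 127 unchanged. It secures survival and contact-based remission status for these subjects; it does not add scheduled imaging after the off-therapy visit.
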